Cover Page

Study Title:

Yttrium-90 Radioembolization for Cirrhosis-Associated Thrombocytopenia

NCT:

NCT03059030

Last reviewed by Northwestern University IRB 4/4/2024

Protocol version 25 dated 5.7.2020

STUDY SUMMARY

Title Yttrium-90 Radioembolization for Cirrhosis-Associated Thrombocytopenia Short Title 90Y for Thrombocytopenia Protocol Number G160096 v. 25 dated 5/7/2020 Phase Pilot study Methodology Open labeled, non-randomized feasibility study Study Duration We estimate it will take approximately 6 years or 72 months to fully enroll and complete the study. Study Center(s) Single Center, Northwestern: (Northwestern University, Northwestern Memorial Hospital) **Objectives** Primary Objective: Evaluate the safety and efficacy of 90Y radioembolization for the management of thrombocytopenia. Number of Subjects 20 Diagnosis and Main Inclusion Criteria Subjects with thrombocytopenia secondary to cirrhosis Study Product(s) TheraSphere® Yttrium-90 Glass Microspheres, BTG International Inc. Duration of administration Dose administered by Interventional Radiologist Statistical Methodology Descriptive statistics will be employed.

STUDY OBJECTIVES

2.1 Primary Objectives

Endpoint #1: Patient safety

The Primary Objective of this pilot study is to evaluate the safety of 90Y RE for the treatment of thrombocytopenia in the setting of cirrhosis. Primary Safety Endpoints include:

1. Assess safety of splenic administration of 90Y. [i.e. the onset of AEs such as infection or abscess as assessed by NCI Common Toxicity Criteria for Adverse Events (CTCAE) Version 4.0.3.)]

2. Assess the utility of splenic 99mTc-MAA injection to determine shunting prior to 90Y RE.

3. Assessment of short-term and long-term post-procedure events

Endpoint #2: Objective clinical endpoints

1. To achieve a 50% increase in platelet count six months after therapy. This will be assessed via CBC with differential at all study visits.

2. To achieve a 20% decrease in functional splenic volume six months after treatment.This will be assessed via cross-sectional CT or MR of the abdomen at screening and at4 weeks, three months, and six months after 90Y infusion.

2.2 Secondary Objectives

1. For patients who are hospitalized after RE, to determine the average length of stay after treatment.

3.0 PATIENT ELIGIBILITY

Subjects must meet all of the inclusion and exclusion criteria to be registered to the study. Study treatment may not begin until a subject is registered.

Inclusion Criteria

Patients must meet the following eligibility criteria at entry:

3.1.1. Male or female, 18 years of age or older, of any ethnic or racial group.
3.1.2. Diagnosis of cirrhosis or portal hypertension with a serum platelet count less than or equal to 80 × 109/L, but no less than 10 × 109/L. [Rationale: platelet count
<100 × 109/L triples the rate of liver- related adverse events (3) and worsens postoperative survival in the setting of HCC (4). Initial platelet count of 80 × 109/L can allow the majority of patients who successfully respond to 90Y-RE (clinical endpoint of 50% platelet count increase) to exceed the 100 × 109/L threshold.]
Cirrhosis is defined by one of three criteria:

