12.5 Safety and Outcome Analysis

Clinical and outcome measures will be compared to baseline. These include platelet count and splenic volume.

Safety measures will be monitored at each study visit. These include the adverse event reporting;

physical examination; and cross-sectional imaging to assess for radio-pathologic findings. MAA will be conducted for the first four patients. The lung shunt study data will be provided to the FDA for review when all 4 patients have completed the lung shunt study before the 5th patient is scheduled for 90Y therapy. If average shunt of first four patients is less than 5%, then all subsequently enrolled patients will not undergo MAA. If average shunt is >5%, the next 6 patients will undergo MAA. If the average shunt among the 10 patients is >5%, then all subsequent patients will undergo MAA. Otherwise, the remaining patients will not receive MAA. In addition to the conventional angiogram, we will perform 3-dimensional rotational angiography/cone beam computerized tomography in all patients. Conventional angiography and cone beam CT essentially eliminate the chance of aberrant deposition of the radioactive microspheres. Subjects who do not undergo pretreatment MAA will undergo post-treatment 90Y PET scan.

Interim Analysis

An interim analysis will be performed after the 10th patient is enrolled. It will include patient registration, treatment and follow-up information including any adverse events and any concomitant medications which were taken due to study treatment and/or procedures per treating investigator. It will summarize the results of the primary and secondary objective clinical endpoints. Any protocol deviations will be listed as well.

STATISTICAL ANALYSIS

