14.1 General Considerations

General considerations: continuous variables will be summarized as n, mean, standard deviation, median, minimum and maximum. Categorical variables will be summarized as the number and percentage of patients in each category.

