14.6 Laboratory evaluations

Summary statistics for baseline and change from baseline will be summarized.

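### Does the entry rationale that most 50% responders will pass 100 × 10⁹/L need support, or a planned count of patients above 100?

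*Combined protocol and SAP*

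**What the plan says.** Section 3.1.2 requires a "serum platelet count less than or equal to 80 × 109/L, but no less than 10 × 109/L". Its bracketed rationale starts from a harm threshold, saying that a count "<100 × 109/L triples the rate of liver- related adverse events (3"). It then argues that an initial count of 80 "can allow the majority of patients who successfully respond to 90Y-RE (clinical endpoint of 50% platelet count increase) to exceed the 100" × 10⁹/L threshold.

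The platelet endpoint, in section 2.1 under Endpoint #2, is relative: "To achieve a 50% increase in platelet count six months after therapy". The same item has platelets measured by CBC at every study visit.

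The analysis is descriptive throughout. Section 14.1 says that "continuous variables will be summarized as n, mean, standard deviation, median, minimum and maximum", and that categorical variables are given as number and percentage. Section 14.6 adds, for laboratory values, that "Summary statistics for baseline and change from baseline will be summarized". Section 12.5 compares platelet count with baseline, and the Interim Analysis paragraph after it says "It will summarize the results of the primary and secondary objective clinical endpoints". None of this text names the number of patients above 100 × 10⁹/L.

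**The concern.** The rationale takes its arithmetic from the highest count a patient may have at entry, yet the criterion reaches down to 10 ("but no less than 10 × 109/L"). A responder who starts well below 80 can meet the 50% endpoint and remain under the level that the protocol treats as clinically important. The reverse also occurs: a patient who starts near 80 can pass 100 without meeting the endpoint.

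So neither the 50% responder rate nor the mean change tells a reader how many patients passed 100. Section 14.2 says the pilot is meant to inform the powering of a later randomized trial, and the proportion above 100 would be a natural figure to carry forward. If the summaries omit it, the pilot would not report on the reasoning behind its own entry limit.

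**Working it through.** **Inputs from the documents.** Eligible baseline 10 to 80 and threshold 100, both × 10⁹/L (section 3.1.2); response taken as a rise of at least 50% at six months (section 2.1); 20 patients (section 14.2). The documents give no baseline distribution and no expected rise, so every distribution and every rise above 50% used below is an assumption.

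**Step 1. The plan's own arithmetic.** At the cap, 80 × 1.5 = 120, which exceeds 100. The sentence holds at the count it names.

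**Step 2. Break-even baseline.** A patient whose count rises by the fraction r passes 100 when baseline > 100 / (1 + r).

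| Rise | Calculation | Baseline must exceed |
|---|---|---|
| 50% | 100 / 1.5 | 66.7 |
| 75% | 100 / 1.75 | 57.1 |
| 100% | 100 / 2 | 50 |
| 150% | 100 / 2.5 | 40 |

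At the minimum rise, the qualifying baselines are the top 80 − 66.7 = 13.3 units of a range of 80 − 10 = 70 units, and 13.3 / 70 = 19%. If all responders rose by the same percentage, *majority* would require their median baseline to lie above the figure in the last column.

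**Step 3. Do endpoint and threshold agree for each patient?** Not always.

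- From 50 to 75 is a rise of 25 / 50 = 50%: a responder, but below 100.
- From 75 to 105 is a rise of 30 / 75 = 40%: above 100, but not a responder.

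The rise needed to reach 100 is 100 / baseline − 1: 25% from 80, 33% from 75, 43% from 70, 100% from 50.

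**Step 4. Can *majority* be settled?** With a normal baseline distribution truncated to 10–80 and one common rise, the share of responders above 100 is the probability that the baseline exceeds the break-even in Step 2. Mean and SD below are those of the normal before truncation.

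| Assumed mean, SD | 50% rise | 75% rise | 100% rise | 150% rise |
|---|---|---|---|---|
| 40, 15 | 3.5% | 12.6% | 25.5% | 51.0% |
| 50, 15 | 11.4% | 30.2% | 49.0% | 74.5% |
| 60, 12 | 25.4% | 57.4% | 78.8% | 95.0% |
| 65, 10 | 39.3% | 76.9% | 92.8% | 99.3% |
| 70, 8 | 62.2% | 94.0% | 99.3% | 100.0% |

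The 50% column is a floor, because it gives every responder the smallest qualifying rise. At a 150% rise all five rows show a majority; at exactly 50% only the last does. The table shows how far the answer depends on inputs the documents do not supply. It does not estimate the true share.

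**Step 5. What depends on the sentence?** The Statistical Considerations section says the 20 patients are there to look for a signal and that no Simon design is used. Section 12.2 gives safety as the main rationale and derives no sample size from an effect. Section 12.5 has a decision rule, but it concerns lung shunt. Neither the platelet endpoint nor any analysis refers to 100.

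**The case for a change.** The best case for a change is that it costs almost nothing. One qualifying clause in section 3.1.2 and one descriptive line under section 14.6 would suffice, with no effect on eligibility, treatment or visits. Naming the threshold in advance would also protect against choosing a cut-off after the results are known, and the figure could serve the later trial.

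Much of this stands. The word *majority* has no support beyond the arithmetic at the cap, since the two citations attached to the rationale concern the harm of low counts. The supplied analysis text does not name the figure, and a count above 100 would be a reasonable addition.

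Three parts do not stand. First, the trial is not prevented from checking its rationale: every patient with a six-month CBC has a count that can be compared with 100, and section 14.1 already provides the number-and-percentage format. Second, the protection against a late choice of cut-off is worth little here, because the protocol already names 100 in section 3.1.2; an analyst who reports that level is not picking it after the fact. Third, the rationale only says what a starting count of 80 can allow. It explains an upper entry limit, and a pilot need not formally test such an explanation.

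Reporting the count separately for baselines above and below 66.7 would add little. That boundary matters only for a rise of exactly 50%, and 20 patients would leave very small cells.

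**Conclusion.** No change to the plan is called for. The observation is accurate in a narrow form: *majority* is supported only by 80 × 1.5 = 120 at the eligibility cap, and a responder with the minimum rise stays at or below 100 from any baseline of 66.7 or less. It does not establish an error, because the share above 100 could be anywhere from 3.5% to practically all responders over the assumptions tried, and the documents contain nothing that narrows this.

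Following the plan as written still gives sound descriptive results on the endpoint it states. The missing count is a gap that an analyst can fill from the CBC data if it is wanted, and rewording the rationale would alter no analysis or conclusion. This judgement rests on reading the endpoint as a rise of at least 50%, and on the supplied text, in which no sample size, test or decision rule uses the 100 × 10⁹/L level. If a later trial were to adopt passing 100 as an endpoint, the baseline distribution and expected rise would have to be stated there.

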3.1.2.1. Liver Biopsy/histology consistent with cirrhotic architectural liver changes

- 3.1.2.2. Portal hypertension (Hepatic venous pressure gradient ≥10 mm Hg)
- 3.1.2.3. Evidence of esophageal and/or gastric varices
- 3.1.3. Patients must have evidence of splenomegaly as determined by Screening crosssectional

imaging.

3.1.4. No evidence of myelosuppression (e.g. lymphopenia) as evidenced by normal hematology values at screening (except in cirrhotic patients).

3.1.5. Adequate baseline organ function as evidenced by normal BUN/Cr and electrolytes on screening chemistry (except in cirrhotic patients).

3.1.6. Eastern Cooperative Oncology Group (ECOG) Performance Status score of 0-2

3.1.7. Patient has a life expectancy of greater than 6 months without intervention.

3.1.8. Patient is willing to participate in the study and has signed the study

informed consent.

3.1.9. Women of childbearing potential must have a negative serum pregnancy test within

28 days prior to screening and must not be breastfeeding.

3.2 Exclusion Criteria

3.2.1. Patients with serum platelet count less than $10 \times 109/L$.

3.2.2. History of bleeding disorder attributed to another cause other than cirrhosis (e.g. von

Willebrand disease)

3.2.3. Declines or unable to provide informed consent

3.2.4. History of prior PSE or splenectomy

3.2.5. Use of any medication known to increase platelet count 1 month prior to Baseline.

3.2.6. History of allergy or sensitivity to TheraSphere[®] or its components.

3.2.7. History of severe peripheral allergy or intolerance to contrast agents, narcotics,

sedatives or atropine that cannot be managed medically

3.2.8. Contraindications to angiography and selective visceral catheterization such as

bleeding, diathesis or coagulopathy that is not correctable by usual therapy or hemostatic agents (e.g. closure device)

3.2.9. Previous randomization in a trial using 90Y RE

3.2.10. Patient must not have participated or enrolled in a clinical trial with an investigational

device / therapy within 30 days prior to randomization

3.2.11. Any serious medical condition likely to impede successful completion of the study,

such as certain mental disorders, cardiac arrhythmias, and uncontrolled

congestive heart failure or respiratory disease.

3.2.12. Patients actively on chemotherapy.

STATISTICAL CONSIDERATIONS

All patients will be accounted for in the final analysis. All patients who discontinue or withdraw after enrollment and before reaching the final follow-up period will be summarized by their reason for discontinuation/withdrawal and will contribute to the analyses as described below and in the statistical analysis plan.

Since this is an exploratory point of care study, the 20 patients are being used to look for a signal. Thus, a Simon's statistical design will not be utilized.

12.1 Trial Design and Objectives

This is an open label, prospective, single-center trial assessing the safety and efficacy of TheraSphere® delivered to the spleen for the treatment of cirrhosis-associated thrombocytopenia. The primary objectives of this trial are to determine the safety of splenic 90Y delivery with TheraSphere®, the improvement in blood platelet count, and reduction in splenic volume.

12.2 Sample Size Determination

As a proof-of-pilot study, the primary rationale is safety. Once the patients are studied, secondary hypotheses may be generated to better refine patient selection and clinical applicability. Though missing data points may occur, statistical analysis will be conducted with the available acquired information.

12.3 Demographics

Descriptive statistics of demographics, medical history, disease severity, time from diagnosis, physical exam, and other baseline characteristics will be presented for all patients.

Efficacy

Descriptive statistical analyses will be used for the safety and efficacy.

12.5 Safety and Outcome Analysis

Clinical and outcome measures will be compared to baseline. These include platelet count and splenic volume.

Safety measures will be monitored at each study visit. These include the adverse event reporting;

physical examination; and cross-sectional imaging to assess for radio-pathologic findings. MAA will be conducted for the first four patients. The lung shunt study data will be provided to the FDA for review when all 4 patients have completed the lung shunt study before the 5th patient is scheduled for 90Y therapy. If average shunt of first four patients is less than 5%, then all subsequently enrolled patients will not undergo MAA. If average shunt is >5%, the next 6 patients will undergo MAA. If the average shunt among the 10 patients is >5%, then all subsequent patients will undergo MAA. Otherwise, the remaining patients will not receive MAA. In addition to the conventional angiogram, we will perform 3-dimensional rotational angiography/cone beam computerized tomography in all patients. Conventional angiography and cone beam CT essentially eliminate the chance of aberrant deposition of the radioactive microspheres. Subjects who do not undergo pretreatment MAA will undergo post-treatment 90Y PET scan.

Interim Analysis

An interim analysis will be performed after the 10th patient is enrolled. It will include patient registration, treatment and follow-up information including any adverse events and any concomitant medications which were taken due to study treatment and/or procedures per treating investigator. It will summarize the results of the primary and secondary objective clinical endpoints. Any protocol deviations will be listed as well.

STATISTICAL ANALYSIS

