14.2 Sample Size Accrual

This is a single center pilot study aiming to evaluate the safety, efficacy, and tolerability of 90Y RE for cirrhosis-associated thrombocytopenia. A small number of subjects will be recruited for this purpose (20 subjects). The first 4 subjects will receive planning angiography and MAA. They will be carefully monitored for adverse events to establish preliminary safety of initial dosing plan. The lung shunt study data will be provided to the FDA for review when all 4 patients have completed

the lung shunt study before the 5th patient is scheduled for 90Y therapy. We estimate it will take approximately 6 years to recruit, treat, and complete follow up on 20 subjects. The results of the study will provide critical preliminary data to later guide in powering a more statistically robust, and larger randomized controlled trial in the future.

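### Does a primary safety endpoint that may rest on only four MAA studies, with no interval and no branch for a mean shunt of exactly 5%, need new text?

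*Combined protocol and SAP*

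**What the plan says.** Section 2.1 of the combined protocol and SAP lists, as the second primary safety endpoint, "Assess the utility of splenic 99mTc-MAA injection to determine shunting prior to 90Y RE". The visible text does not define utility further.

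Section 12.5 gives MAA to the first four patients and then sets two stages.

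- Stage one, stop: "If average shunt of first four patients is less than 5%, then all subsequently enrolled patients will not undergo MAA".
- Stage one, continue: "If average shunt is >5%, the next 6 patients will undergo MAA".
- Stage two: a mean above 5% among the ten sends every later patient to MAA. "Otherwise, the remaining patients will not receive MAA".

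The same section sends the shunt data to FDA before patient 5 is scheduled and has cone beam CT done in everyone. It adds: "Subjects who do not undergo pretreatment MAA will undergo post-treatment 90Y PET scan".

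The analysis text is generic. Under the Efficacy heading that follows 12.3: "Descriptive statistical analyses will be used for the safety and efficacy". In 14.1: "continuous variables will be summarized as n, mean, standard deviation, median, minimum and maximum". Section 14.2 expects the results to "provide critical preliminary data to later guide in powering a more statistically robust, and larger randomized controlled trial".

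**The concern.** An endpoint whose sample size is set by its own result deserves a second look. If the first four shunts average below 5%, collection stops and the reported mean is below 5% because the rule says so. A later reader could take that as an independent finding. Sections 12 and 14 name no confidence interval, do not say at which stage the endpoint is reported, and do not say what would show that MAA was useful. On the visible text no patient is said to have both MAA and 90Y PET, so it is unclear whether utility means the size of the shunt or its agreement with later 90Y deposition.

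The stage-one wording also covers only means below and above 5%. A mean of exactly 5% belongs to neither branch, whereas the default at stage two picks it up.

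At stake is whether a result from four patients would look firmer than it is when a larger trial is planned.

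**Working it through.** **Inputs.** From 12.5: 4 patients at stage one, 6 more at stage two, threshold 5%. From 14.2: 20 patients in all. The documents give no shunt mean or SD and no sample size for this endpoint, so there is no planned figure to reproduce.

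**Branches.** Assuming all 20 enrol and every scheduled MAA is done, the number of studies is 4, or 4 + 6 = 10, or 20.

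**Precision.** The half-width of a 95% t interval, in SD units, is t(0.975, n−1)/√n:

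- n = 4: 1.591
- n = 10: 0.715
- n = 20: 0.468

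For example, shunts of 3, 4, 5 and 6% have mean 4.5 and SD 1.29. They stop at stage one, with interval 4.5 ± 1.591 × 1.29, or 2.4 to 6.6%. Every ingredient of that interval (n, mean, SD) is already in the 14.1 summary.

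**Effect of the stopping rule.** This needs an assumed distribution. I took lognormal shunts with SD from half the mean to equal to the mean, 500,000 cohorts of 20 per setting: stop at 4 if the mean of four is below 5, otherwise stop at 10 if the mean of ten is at most 5, otherwise continue to 20.

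| True mean / SD (%) | P(stop at 4) | P(reach 20) | Average mean of four, given stop (%) | Coverage of t interval, given stop |
|---|---|---|---|---|
| 3 / 1.5 | 98.5% | 0.0% | 2.96 | 92.1% |
| 3 / 3 | 91.0% | 1.9% | 2.66 | 84.8% |
| 4 / 2 | 85.0% | 4.0% | 3.70 | 91.4% |
| 4 / 4 | 76.8% | 10.8% | 3.15 | 82.1% |
| 5 / 2.5 | 55.0% | 31.8% | 4.11 | 86.8% |
| 5 / 5 | 59.9% | 27.9% | 3.47 | 77.3% |
| 6 / 3 | 26.9% | 68.7% | 4.34 | 73.7% |
| 6 / 6 | 44.0% | 47.5% | 3.70 | 68.9% |

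A gamma model (200,000 cohorts) agrees in direction. At a true mean of 5% with SD 2 or 4, the chance of stopping at four is 53% or 56%, and the final mean is biased by −0.34 or −0.67 points.

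Three readings follow.

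1. At a true mean of 3% the distortion is at most 3 − 2.66 = 0.34 points. It becomes large only when the true mean is near or above 5%, and nothing in the documents suggests that it is.
2. The first four patients have MAA whatever their values, so the four observations are not selected. Only a report conditional on having stopped is.
3. Adding a t interval would not repair this. At a true mean of 3% its coverage is 85 to 92% among stopped cohorts and 86 to 92% over all cohorts, so there the shortfall comes from skewness at n = 4, and a label saying the interval ignores the stopping rule would not disclose it. At 6% coverage falls to 69 to 74%. Among cohorts stopped at four, the lower limit is below zero, an impossible shunt, in 43 to 53% when SD equals the mean and 6 to 12% when SD is half the mean.

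**Exactly 5%.** The four values must sum to exactly 20. Under the same lognormal settings the chance is 0.8 to 8.1% if shunts are recorded in whole percent and 0.07 to 0.8% at one decimal. The recording precision is not stated.

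**The case for a change.** The strongest argument for a change is that it would cost a few sentences and no patient, visit or procedure. This is a primary safety endpoint, the results are meant to inform a larger trial, and a mean below 5% can merely restate the rule that ended collection. FDA review is a review step, not an endpoint analysis. The interim analysis after the tenth patient covers the objective clinical endpoints, which in 2.1 is the heading for platelets and splenic volume, and does not name MAA.

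All of that is accurate as description. What stands is that a good report would list the shunts per patient, say at which stage MAA stopped, and remark that a stage-one mean is below 5% by design. But 14.1 already forces n into the report, and with full accrual an n of 4, 10 or 20 identifies the stage. The range of four values printed beside it makes it hard to over-read the mean. Section 14.2 does not name shunt as an input to the later trial's sample size.

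The missing definition of utility is real in the visible text, but sections 4 to 11 and 13 are not shown and may describe the MAA and PET procedures. Section 12.5 requires PET for patients without MAA; it does not say that MAA patients go without PET.

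**Conclusion.** No change to the plan follows. The branch counts of 4, 10 and 20 are right, and so are the gap at exactly 5% and the absence of a visible definition of utility. None of these alters a planned result. An added interval is a reporting preference in a descriptive pilot, can be computed from what 14.1 already requires, and in its standard form would under-cover (69 to 74% at a true mean of 6%, for stopped cohorts). Writing down what utility means is a gap that analysts would fill sensibly, and whether it is a gap at all depends on sections not shown. The exact-5% case is a small wording slip: under 1% likely at one-decimal recording and up to 8.1% at whole-percent recording. It would come to light when FDA receives the data before patient 5 is scheduled; which branch applies is for the sponsor and FDA to settle.

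The simulated figures rest on assumed shunt distributions with true means of 3 to 6%. The structural points need no such assumption beyond full accrual and completion of every scheduled MAA. Whether waiving MAA is sound is a clinical question and is not judged here.
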